**Overview**

For Aim 5 80 (ages 25-65) Gold 0-2 subjects that are current smokers (defined by PFTs, questionnaires and interviews as discussed below) will be recruited. Participants will be equally distributed between males and females and will be representative of the national racial/ethnic populations. Subjects will be recruited using advertisements, email blasts, smoking cessation clinic and physician referrals. Participants that are enrolled into the study will have a total of 4 visits (baseline, 30 day, 60 day and 90 day) over 3-4 months. During the study visits, subject will have vitals, blood tests, urine sample, CT scans, pulmonary function tests, and complete questionnaires. Subjects will also participate in a smoking cessation program. Subjects will be contacted weekly, by phone, for smoking cessation follow up.

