### ***Blood and Urine Collection***

Blood samples will be taken to test the subject's creatinine, cotinine and C-reactive protein level. Two additional tubes of blood will be drawn for serum and plasma collection (baseline and 90 day visit). The creatinine level will only be tested prior to the contrast CT (baseline visit and 90 day visit). The cotinine and C-reactive protein level will be tested at baseline, 30 day, 60 day, and 90 day visits. Women of child bearing potential (WOCBP) will have a urine pregnancy test.

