### ***Smoking Cessation***

Subjects will enter a 3-month smoking cessation program overseen by [name] and [name] who run the hospital-based smoking cessation program. [name] study coordinator will work full time in cooperation with the University of Iowa Hospitals and Clinics Smoking Cessation Clinic in the Pulmonary Rehabilitation Program to maximize success rate. The clinic operates under the Surgeon General's Clinical Practice Guideline Treating Tobacco Use and Dependence: 2008 Update. The study team will meet with the subject in person at the baseline, 30 day, 60 day and 90 day visits and follow up by phone weekly. At the baseline visit the subject will be asked to taper down their use of tobacco for the first week in the study prior to their commitment to quit smoking for the remainder of the study.

Follow up will seek to identify problems already encountered and potential challenges in the immediate future, assessment of current medication use and problems, and restatement of resources to help support them during their tobacco use cessation such as quit-line support.

If tobacco use has occurred, a review of the circumstances and encouragement to recommit to total abstinence will be done.

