### ***Randomization***

Subjects will then be randomized to either Sildenafil, 20 mg orally 3x/day, or Placebo in equal numbers after beginning the smoking cessation program above.

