
Statistical Analysis

For outcome variables that meet a normal distribution error assumption (or are suitable to normalization through a transformation) our statistical analysis for Aims 1-4 will be primarily based on general linear models with identity link and normality of errors. Specifically, we will look at increasing/decreasing trends of the outcome variable as well as pair-wise comparisons across groups. These pair-wise comparisons will be obtained as orthogonal contrasts within the linear models. For those variables that do not meet the assumptions of the general linear models

we will use generalized additive models (GAM). These regression models allow for exploration of nonparametric relationships of an outcome variable with a number of independent variables simultaneously and identify associations when the response variable is not normally distributed or equal variance assumptions are not met. PBV measures will also be assessed using Bland-Altman methods, with adjustment for heteroscedasticity if present. For comparisons that involve an intervention (e.g., hypoxia and Sildenafil), differences between study groups will be estimated by a time (pre/post)*group interaction term in linear models with generalized estimating equations.

All models will be adjusted for covariates. Covariates will be considered for inclusion into regression models based principally on plausible evidence and secondarily on evaluation of statistical associations in the dataset. Data from multiple scans of the lung of a subject are generally spatially and/or temporally correlated; we will account for such correlation in the analysis, e.g. as random effects in a linear mixed model (113) Since a major interest in this study is to investigate differences between ordinal groups we perform pair wise comparisons between groups. To control the experiment-wise type I error (“multiple comparisons”), we use the Holm step-down procedure, an improved version of the Bonferroni criterion. Subject dropout and resultant missing data in the smoking cessation project will use the Generalized Estimating Equation GEE to impute the missing values for our generalized linear model analysis of the data.

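### Aim 5: the covariate rule for the sildenafil-placebo comparison is not limited to baseline variables, so a covariate affected by treatment could enter and bias the arm effect

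*SAP*

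**What the plan says.** The SAP's Statistical Analysis section states that "All models will be adjusted for covariates". The selection rule follows: covariates are to be considered principally on plausibility and "secondarily on evaluation of statistical associations in the dataset". No covariate is listed. No selection threshold is given, nor any timing relative to unblinding or restriction to variables measured before randomisation.

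For interventions, with sildenafil given as an example, "differences between study groups will be estimated by a time (pre/post)*group interaction term in linear models with generalized estimating equations". The same section expects dropout in the smoking cessation project and proposes to handle it through GEE.

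The Protocol (Randomization) makes the comparison a randomised one: "Subjects will then be randomized to either Sildenafil, 20 mg orally 3x/day, or Placebo in equal numbers". Several variables that could serve as covariates are measured after that point:

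- **Exhaled CO and serum cotinine:** the Schedule of Study Assessments and Procedures has both at the 30, 60 and 90 day visits.
- **CRP:** Blood and Urine Collection says "The cotinine and C-reactive protein level will be tested at baseline, 30 day, 60 day, and 90 day visits". The Schedule shows CRP at baseline and 90 days only. The two should be reconciled, but either gives a post-randomisation value.
- **Tobacco use:** under Smoking Cessation, the study team will also "follow up by phone weekly".

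**The concern.** In a randomised comparison, baseline covariates can improve precision without changing the question. A variable measured after randomisation is different. If treatment affects it and it lies on the path to the outcome, adjusting for it removes part of the effect. If treatment affects it and it merely shares a cause with the outcome, adjusting for it can create an apparent effect where none exists.

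The SAP's rule does not separate these cases. In a smoking-cessation trial with lung perfusion and density outcomes, smoking exposure and inflammation are easy to call plausible. They may also be associated with the outcome in the data, so neither criterion keeps follow-up cotinine, exhaled CO or CRP out of the arm comparison. The validity of the Aim 5 estimate is at stake, together with some precision if the baseline outcome is not used well.

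**Working it through.** **Inputs.** The Protocol Overview gives the size ("For Aim 5 80 (ages 25-65) Gold 0-2 subjects that are current smokers"), so equal allocation means 40 per arm. The model is the SAP's time-by-group term. The documents state no alpha, power, effect size, SD, correlation or dropout rate, so there is no planned figure to reproduce. Everything below on the SD scale is an assumption. For scale, at an assumed two-sided alpha of 0.05 and 80% power, the detectable difference is (1.96 + 0.84) × √(2/40) ≈ 0.63 SD.

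**1. Does screening baseline covariates on the data inflate type I error?** Simulation of change from baseline with 40 per arm and no treatment effect. There were 4, 6 or 8 independent baseline candidates, each with slope 0.2, and a candidate entered if p < 0.10 with the outcome, blind to arm.

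| Candidates | No covariates | Blind screening |
|---|---|---|
| 4 | 5.8% | 5.4% |
| 6 | 5.0% | 5.0% |
| 8 | 4.8% | 5.0% |

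It does not.

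**2. What can move the time-by-group term?** With two time points and complete data, the term is the difference between arms in mean change. A covariate that is constant over time and enters as a main effect cancels out of each subject's change. One simulated dataset (GEE, exchangeable, n = 80) shows this:

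| Model | Estimate | SE |
|---|---|---|
| time × group | 0.0835 | 0.349 |
| + baseline main effect | 0.0835 | 0.349 |
| + baseline covariate × time | 0.175 | 0.358 |
| + time-varying covariate | 0.138 | 0.344 |
| 25% of follow-up missing, no covariate | -0.093 | 0.362 |
| 25% of follow-up missing, + baseline main effect | -0.052 | 0.357 |

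This shows which routes are open, not how large the shifts would typically be.

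**3. Covariate on the causal path.** Let treatment shift the covariate by a, the covariate act on the outcome with slope b, and the direct effect be 0.3 SD. The total effect is 0.3 + a × b, and the adjusted estimate targets 0.3.

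- a = 0.3, b = 0.3: total 0.39, so 0.09/0.39 = 23% is removed (simulated 24%).
- a = 0.8, b = 0.5: total 0.70, so 0.40/0.70 = 57% is removed (simulated 58%).

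**4. Covariate affected by treatment that shares a cause with the outcome, true effect zero.** If the within-arm slope of outcome on covariate is s (unit SDs), the adjusted arm effect has bias -a × s. Take s = 0.5.

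- a = 0.3: bias -0.3 × 0.5 = -0.15 SD. SE = √(0.75 × 2/40 × (1 + 0.3²/4)) = 0.196, bias/SE = 0.77, rejection rate about 12% (simulated 13%).
- a = 0.6: bias -0.6 × 0.5 = -0.30 SD. SE = √(0.75 × 2/40 × (1 + 0.6²/4)) = 0.202, bias/SE = 1.48, rejection rate about 32% (simulated 31%).

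Here 0.75 = 1 - 0.5² is the residual variance. A wider simulated grid (a of 0.5 and 0.8, s of 0.25 and 0.64) gave bias of -0.13 to -0.51 SD and type I error of 9% to 77%.

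**5. Gain from using the baseline outcome properly.** With equal pre and post variances and correlation ρ, the ANCOVA variance divided by the change-score variance is (1 - ρ²)/(2(1 - ρ)) = (1 + ρ)/2. That is 0.65 at ρ = 0.3 and 0.85 at ρ = 0.7 (simulated 0.66 to 0.87).

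**The case against.** The strongest reply has four parts.

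**The rule is milder than it sounds.** Data associations are expressly secondary to plausible evidence, and covariates are only considered for inclusion. A reader might infer that choosing covariates from the data by itself inflates type I error or lets the result be steered. The documents do not support that. Arm-blind screening holds the nominal level (step 1), and with complete data baseline main effects cannot move the planned term (step 2). Inflation from selection would require choosing the covariate set on the arm p-value, which the SAP does not describe. This part of the reply stands in full.

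**Smoking markers may not be affected by sildenafil.** Both arms receive the same cessation programme, and nothing in the documents says the drug changes smoking. Adjusting for a covariate that treatment leaves alone does not remove the effect: in a simulated check with a true effect of 0.60, the adjusted mean was 0.598. This stands as a limit, because the bias in steps 3 and 4 needs treatment to affect the covariate. CRP is the more plausible case. Whether treatment affects such a variable would not be known beforehand, which is the reason to exclude it by rule.

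**The rule was written for observational comparisons.** Much of the section concerns Aims 1-4 and ordinal groups, where such a rule is ordinary. But it covers all models, and the same section includes sildenafil among the interventions. Part of the SAP was not in the text available for review, so a separate Aim 5 rule cannot be excluded.

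**A baseline list would change nothing.** As main effects in the planned GEE with complete data, that is correct. It is an argument for specifying how the covariates enter, not for leaving the rule open.

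**Conclusion.** The concern holds in a limited form. The plan's covariate rule reaches the randomised Aim 5 comparison and does not exclude post-randomisation variables, several of which are collected. The exposure comes through post-randomisation or time-varying covariates, covariate-by-time terms and dropout, not through data-driven screening of baseline variables as such.

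Under the assumptions of step 4, the bias is -0.15 to -0.30 SD. That is about a quarter to a half of the roughly 0.63 SD that 40 per arm could detect (0.15/0.63 = 24%, 0.30/0.63 = 48%). If the covariate mediates the effect, about 24% to 58% of the effect could be removed. These figures illustrate the possible size and are not predictions. They depend on correlations that the documents do not give, and they fall to zero if treatment does not affect the covariate. It is also assumed that the SAP's time-by-group term is the intended arm comparison.

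**What to change.** For Aim 5, replace the general rule with the following, settled before unblinding:

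1. A short fixed list of baseline covariates that includes the baseline value of the outcome. The others are the sponsor's choice from variables already collected.
2. A statement of how they enter. Baseline is already the pre response in the GEE, so the baseline outcome should be used through ANCOVA on the follow-up value or through baseline-by-time terms. A main effect alone would leave the contrast unchanged with complete data.
3. No post-randomisation covariate in the primary arm comparison.
4. Data-driven or post-baseline adjustment (cotinine, exhaled CO, CRP, reported tobacco use) confined to models labelled exploratory.

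No new data are needed. The cost is slightly more than wording, because item 2 changes how the model is specified. In return, the variance of the arm effect falls to about 0.65 to 0.87 of the change-score variance at assumed pre/post correlations of 0.3 to 0.7. The present rule can stay for the observational comparisons in Aims 1-4.

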### ***CT Scans***

A subject may undergo 13 total low-dose scans throughout the study within 3 months:

**Baseline Visit:** 3 low-dose non-contrast CT volumetric research scans (TLC, FRC, RV) and 2 low-dose dual-energy contrast CT research scans at FRC.

**30-day Visit:** 2 low-dose non-contrast CT Volumetric research scans (TLC, RV)

**60-day Visit:** 2 low-dose non-contrast CT Volumetric research scans (TLC, RV)

**90-day Visit:** 3 low-dose non-contrast CT Volumetric research scans (TLC, FRC, RV) and 1 low-dose dual-energy contrast CT research scan at FRC.

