Image Quantitation and Outcome Measures: Lung density histogram-based measures of parenchymal characteristics and PBV parameters extracted using the Siemens software for material decomposition will serve as the primary metrics in this project. Regional PBV will be expressed as a percent of the total lung PBV. The primary outcome measure in this study will be CV of PBV and regional ventilation along with neutrophil accumulation assessed by SPECT. The primary measure used to assess lung parenchyma in the non-contrast scans will be the percent of lung falling below -950 HU. Secondary measures include the position of the lower 15th percentile point on the lung density histogram (P15) and “Alpha” negative of the slope of the log-log plot of the number of holes plotted against hole size (44) with holes defined as connected voxels < -950 HU. In all of the volume scans we will extract the lungs, lobes, sub-lobe segments, airway tree out to two generations beyond the segmental airways as outlined in (1) in addition to assessing CV of PBV and ventilation (from image matching) and lung density measures for completeness of lung characterization. From the image matching, we will have lung density on a region-by-region basis at an acinar level of detail. Based upon density changes within a known regional volume of lung, we have a measure of regional ventilation. In the Sildenafil study, change in DLCO (pre and post Sildenafil) will serve as a secondary outcome measure with the expectation that as inflamed lung regions are perfused, DLCO will drop but that this will recover in the smoking cessation follow-up and will correlate with a drop in total lung density on the TLC scans. In addition to evaluating CV of PBV and ventilation, we will warp pre and post hypoxia and Sildenafil PBV image sets and test whether the regions of highest PBV remain high under hypoxia in the emphysema susceptible smokers and whether the regions of low PBV increase with Sildenafil. This test will significantly strengthen the link back to our primary hypothesis. Image matching software developed in house (53, 55-59) will be used to correlate data from the non-contrast volume scan and the PBV DECT scan. Heterogeneity of PBV will be assessed using our in-house PASS software. All other analysis will be assessed via VIDA’s (Software derived from our laboratory and now commercialized and FDA 510K cleared) Apollo software. The VIDA software together with PASS has analyzed over 50,000 CT data sets from a growing number of multi-center investigations. Details of analysis approaches are given in (1). Segmentation results are passed between Apollo and PASS. In PASS, we are able to use the vascular tree extracted by Apollo to identify the vascular paths that serve to define the sub-lobe segments. We will use these lobar and sub-lobe demarcations as the basis for evaluating PBV heterogeneity and lung density metrics in the emphysema susceptible and emphysema-free normal smokers.

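### The SAP has GEE impute dropout data, which GEE does not do; one of three possible readings usually understates the standard error, so the sentence should say which is meant

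*SAP*

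**What the plan says.** The last sentence of the SAP's Statistical Analysis section gives the missing-data rule: "Subject dropout and resultant missing data in the smoking cessation project will use the Generalized Estimating Equation GEE to impute the missing values". The same sentence then states where those values are to go, namely into a second model: "for our generalized linear model analysis of the data". Earlier in that section GEE already has a different role. For comparisons involving an intervention, "differences between study groups will be estimated by a time (pre/post)*group interaction term in linear models with generalized estimating equations". The section also says "All models will be adjusted for covariates".

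The project the rule refers to appears to be the randomized sildenafil trial. In the protocol, "Subjects will enter a 3-month smoking cessation program" (Smoking Cessation), and subjects are then allocated to sildenafil "or Placebo in equal numbers after beginning the smoking cessation program above" (Randomization). The SAP's section on image quantitation and outcome measures places the cessation follow-up inside the sildenafil study, where it expects that "DLCO will drop but that this will recover in the smoking cessation follow-up".

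For perfused blood volume (PBV), the protocol's CT Scans section schedules two contrast scans at baseline and, at day 90, "1 low-dose dual-energy contrast CT research scan at FRC". No contrast scan is scheduled in between.

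**The concern.** GEE has no step that produces replacement values. A programmer given this sentence must decide what it means, and three decisions are possible:

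1. Fill each missing value with its GEE fitted mean and analyse the completed data.
2. Carry out a proper multiple imputation and analyse the imputed sets.
3. Fit GEE to all observed records and fill in nothing.

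Readings 2 and 3 are valid under random dropout. Under reading 1 the filled values count as if observed, so the standard error is usually too small. The readings can give different p-values for the sildenafil-placebo comparison, so the choice should be fixed before unblinded data are seen. A subject lost before day 90 has no follow-up PBV value, so the rule bears on a primary metric.

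**Working it through.** There is no stated figure to reproduce.

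**Inputs from the documents.** 80 subjects (protocol, Overview) in equal numbers (Randomization): 80 / 2 = 40 per arm. Model: time-by-group term by GEE (SAP, Statistical Analysis).

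**Assumed inputs.** Two-sided 5% test at 1.96; dropout d of 10 to 40%; pre/post correlation r of 0.3 to 0.9; outcome SD 1; no true effect; one baseline and one day-90 value per subject.

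**Reading 1, independence fit, random dropout.** Missing day-90 values receive the observed arm mean. Per arm, times n:

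- True variance of the refitted change: 1 + 1/(1−d) − 2r.
- Variance that the robust formula reports: (1−d)(2−2r) + d.

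Multiplying the first by (1−d) gives 2 − d − 2r + 2rd, which equals the second. The reported variance is therefore (1−d) times the true one at any r, and type I error is 2[1 − Φ(1.96√(1−d))]:

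| d | 10% | 20% | 30% | 40% |
|---|---|---|---|---|
| Type I error | 6.3% | 8.0% | 10.1% | 12.9% |

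**Reading 1, exchangeable fit.** The filled mean is adjusted for the baseline of those lost. The reported variance is as above. The true variance times n is 1 − 2r + (1 + d³r² − 2d²r²)/(1−d).

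- At d = 0.2, r = 0.5: true 0 + 0.982/0.8 = 1.2275; reported 0.8 + 0.2 = 1.0; ratio 0.815; type I error 7.7%.
- At d = 0.2, r = 0.9: true −0.8 + 0.94168/0.8 = 0.377; reported 0.16 + 0.2 = 0.36; ratio 0.955; type I error 5.5%.
- At r = 0.9 across d = 10, 20, 30, 40%: 5.6, 5.5, 5.3, 5.0%.

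**Simulation, random dropout** (20,000 runs per cell, r = 0.3 to 0.9, robust SE without small-sample correction), type I error:

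| Dropout | Fill, independence | Fill, exchangeable | GEE on observed records |
|---|---|---|---|
| 10% | 6.8–7.1% | 6.2–7.1% | 5.5–5.9% |
| 20% | 8.6–9.2% | 6.5–9.0% | 5.4–6.2% |
| 30% | 10.7–11.5% | 6.1–11.0% | 5.2–6.0% |
| 40% | 13.7–14.4% | 5.9–14.1% | 5.4–6.4% |

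With no dropout the same test gives 5.4 to 6.1%, so the small excess in the last column is a small-sample effect. Smaller runs (3,000 and 6,000 per cell) at 20% dropout gave 7.7 to 9.5%, 5.9 to 9.2% and 5.0 to 6.8% for the three columns. The rounded ranges in the verdict allow for this. Adding four covariates left fill-and-refit at 7.9 to 9.1% at 20% dropout.

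**Reading 2.** Multiple imputation from baseline by arm, 10 imputations, Rubin's rules, 4,000 runs, at 10, 20 and 40% dropout: type I error 4.8, 5.2, 5.3% at r = 0.5 and 5.7, 5.8, 5.3% at r = 0.9. No inflation of note.

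**Does reading 3 need a stated working correlation?** Suppose 20% dropout depends on the baseline value, with a log-odds slope of 1 per SD in opposite directions in the two arms (4,000 runs, observed records only):

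| r | Independence: bias, type I error | Exchangeable: bias, type I error |
|---|---|---|
| 0.5 | −0.18 SD, 10.6% | −0.01 SD, 5.3% |
| 0.8 | −0.27 SD, 30.1% | −0.01 SD, 6.5% |

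Further runs with dropout of this kind, r = 0.5 to 0.9, gave 13 to 57% with independence and 6.5 to 8.1% with exchangeable. So fitting GEE to observed records is not a safe instruction until the working correlation is named.

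**The case against.** The strongest objection is that the sentence is loosely worded and nothing more. It says only that values are imputed. It does not say they are filled in once, nor that they are fitted means without added variation. Multiple imputation fits the words equally well and keeps the error rate near 5%. This stands. A reader might infer that the SAP commits the trial to a single fill, or that following it necessarily makes false positives rise with dropout. The text does not support the first. The second fails even within reading 1, since with an exchangeable fit at correlation 0.9 the formula falls slightly as dropout grows.

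A second objection also stands: tying the time-by-group term to the sildenafil-placebo change from baseline to day 90 is an inference. The SAP names hypoxia and sildenafil together and speaks of measurements before and after sildenafil. The protocol's schedule footnotes place a pre-dose scan, a 60-minute post-dose scan and a repeat DLCO on the baseline day. The term may be meant for that same-day contrast, where dropout hardly arises.

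Third, at 10% dropout the gain is small, and the uncorrected robust standard error is itself slightly too small at 40 per arm. Both are true, and the second is a reason to add a correction.

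Fourth, the calculations cover outcomes with one baseline and one day-90 value, such as PBV. Non-contrast CT is scheduled at all four visits, and no four-visit case was examined.

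Finally, part of the SAP was not in the text available for review. The lack of a dropout rate, significance level or correlation there cannot be held against the plan. What remains is that the one missing-data sentence in view gives GEE a task it does not perform and leaves the analyst to choose.

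**Conclusion.** The concern holds as a needed clarification with a possible effect on the error rate. The sentence has three readings, and one of them usually understates the standard error. Under that reading, at 20% random dropout, type I error is about 8 to 9.5% with an independence fit and about 6 to 9% with an exchangeable fit, against about 5 to 6% for GEE on observed records. If the authors meant observed-record GEE, the edit only makes the text say so.

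These sizes rest on the assumed dropout rate, correlation and test level, and on dropout being random. They illustrate the risk and do not forecast it. A reader might also infer that observed-record GEE removes all dropout bias. It does not. If dropout depends on the unseen day-90 value (20% dropout, r = 0.5, opposite directions by arm), the exchangeable fit is biased by −0.27 SD, and the likelihood estimator tested alongside it is biased by the same amount.

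**What to change.** Replace the last sentence of the SAP's Statistical Analysis section with:

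> In the primary analysis missing values are not filled in. The sildenafil-placebo comparison from baseline to day 90 uses the time*group GEE model, fitted to all observed records with an exchangeable working correlation and robust standard errors with a small-sample correction. This assumes that dropout depends only on observed data and that the working correlation is approximately right.

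The sponsor should confirm that this is the contrast the time-by-group term is meant to cover and, if it is not, name the model for the day-90 comparison. An independence working correlation should not be used, because baseline-dependent dropout that differs by arm would then bias the comparison.

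Optional sensitivity analysis: multiple imputation by arm, using the day-30 and day-60 cotinine and exhaled CO already in the schedule, combined by Rubin's rules. It is a check and not a cure. In simulations where relapse drove dropout in one arm only, it reduced the bias in part, and it cannot help for a subject who leaves before the first of these measurements.

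Cost: one replaced sentence, a little programming, and slightly wider confidence intervals than a single fill would give. No new data are needed.
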